## 4 ANALYSIS POPULATIONS

The populations that will be included in the analysis are defined below:

- The Full Analysis Set (FAS) comprises all patients to whom study treatment has been assigned. All analysis described in this document, except of AEs analysis (section 9) will be performed with this population.
- The Safety Set (SS) includes all patients who received at least one dose of study treatment. Only AEs analysis (section 9) will be performed with this population.
- Per-Protocol Set (PPS) consists of a subset of the patients in the FAS who are compliant with requirements of the clinical study protocol.

## 5 SCREENING FAILURES

It will be described the number of screening failure patients. And for these patients, the reason:

- Why was the patient not eligible for enrollment? (Did not meet the inclusion criteria / Did not meet the exclusion criteria / Unacceptable or past medical history-concomitant diagnosis / Intercurrent medical event/ Adverse event / Unacceptable laboratory value(s) / Unacceptable test procedure result(s) / Death / Unacceptable use or excluded medication(s)-therapies / Patient withdrew consent / Physician decision / Lost to follow-up / Unknown).

In case of “Did not meet the inclusion criteria”, specify the criteria.

In case of “Did not meet the exclusion criteria”, specify the criteria.

## 6 DESCRIPTIVE ANALYSIS (SCREENING VISIT)

**This section will be analyzed with Full Analysis Set population.**

### 6.1 Recruitment Period

The dates of inclusion of the first and last patient will be provided.

### 6.2 Demography

The continuous variable to be described is:

- Age (years), time from year of birth to year of signed the informed consent.

The categorical variables to be described are:

- Sex (Male / Female). In case of female, Female of childbearing potential? (No / Yes).
- Race (Caucasian / Asian / Black / Other). In case of other, specify.

### **6.3 Medical history**

It will be shown a list with all relevant medical history not related to the study indication

### **6.4 Underlying disease history**

The categorical variable to be described is:

- Diagnosis (Acute myeloid leukemia / Acute lymphoblastic leukemia / Myelodysplastic syndromes / Non-Hodgkin's lymphoma / Hodgkin's lymphoma / Monoclonal gammopathy-Multiple Myeloma / Bone marrow failure-aplastic anemia / Myelofibrosis / Chronic myelogenous leukemia / Chronic myeloproliferative disorders / Others). In case of other, specify.

### **6.5 Description of the transplant**

The continuous variable to be described is:

- Donor age (years).
- Time from transplantation date to start treatment date (months).

The categorical variables to be described are:

- Donor chimerism in peripheral blood (%).
- Donor chimerism in peripheral blood (Total blood / Myeloid compartment).
- Transplant type (Matched family donor / Matched unrelated donor / Mismatched family donor / Mismatched unrelated donor / Haploidentical family donor / Unrelated umbilical cord blood / Other). For every option, it will be describe the family donor (Brother / Sister / Father / Mother / Daughter / Son / Other).
- Source of graft cells (Bone marrow (BM) / Peripheral blood stem cells (PBSC) OBM + PBSC / Umbilical cord blood).
- Poor graft function type (Primary / Secondary).

## 6.6 Conditioning regimen

It will be shown a multiple response table with the following options:

- Cyclophosphamide
- Fludarabine
- Busulfan
- Melphalan
- Thiotapec
- Body irradiation
- Other

## 6.7 Cytogenetic

The categorical variables to be described are:

- Has been a local conventional cytogenetics or FISH performed at screening? (No mandatory, there was one available post-transplant (within 8 weeks before Day 1) / Yes).
- Were the cytogenetic results obtained by conventional cytogenetics or by FISH? (Conventional cytogenetics / FISH).
- Results (Negative for clonal abnormalities / Positive for clonal abnormalities)

■

[figure not shown]
■

■

■

■

■

## 6.9 ECG evaluation

The categorical variables to be described are:

- Has been the ECG performed? (Yes / No). In affirmative case,
  - Overall interpretation (Normal / Clinically insignificant abnormality / Clinically significant abnormality).
  - Prolongation of QTc-interval (No / Yes).

## 6.10 Ophthalmologic monitoring

The categorical variables to be described are:

- Has been the ophthalmologic monitoring performed? (Yes / No). In affirmative case,
  - Retin (Normal / Abnormal).
  - Vessels (Normal / Abnormal).
  - Optic disc/nerve (Normal / Abnormal).
  - Cataracts (No / Yes). In affirmative case,
    - Slit-lamp exam performed? (No / Yes). In affirmative case,
      - Slit-lamp exam (Normal / Abnormal).

## 6.11 Karnofsky performance status

[figure not shown]
The categorical variable to be described is:

- KPS (100% / 90% / 80% / 70% / 60% / 50% / 40% / 30% / 20% / 10%).

## 6.12 Anthropometric data / vital signs

The categorical variable to be described is:

- Has been the anthropometric data/vital signs evaluated? In affirmative case, the continuous variables to be described are:
  - Weight (kg).
  - Height (cm).
  - Sitting pulse (beats/minute).
  - Sitting systolic blood pressure (mmHg).
  - Sitting diastolic blood pressure (mmHg).
  - Respiratory rate (breaths/minute).
  - Body temperature (°C).

### 6.13 Laboratory evaluation

#### **HEMATOLOGY**

The continuous variables to be described are:

- Neutrophils (/µL)
- Platelet count (/µL)
- Hemoglobin (g/L)

In addition, it will be shown:

- Number of patients with <20000 platelets, <1000 neutrophils and <100 hemoglobin.
- Number of patients with <20000 platelets, <1000 neutrophils and >100 hemoglobin.
- Number of patients with <20000 platelets, >1000 neutrophils and <100 hemoglobin.

#### **IMMUNOSUPPRESSANTS DRUGS LEVELS**

The categorical variable to be described is:

- Has been the Immunosuppressants drugs levels performed? (No / Yes). In affirmative case, the continuous variables to be described are:
  - Tacrolimus (ng/mL).
  - CsA (ng/mL).
  - Other (specify).

### 6.14 Blood smear

[figure not shown]
The categorical variables to be described are:

- Has been a blood smear performed and analysed for morphological abnormalities? (No / Yes).
- Has been the percentage of schistocytes determined? (No / Yes). In affirmative case, it will be shown the percentage schistocyte (%).

[figure not shown]
## 7 END OF STUDY FORM

The categorical variable to be described is:

- Did the patient complete the study? (No / Yes). In negative case, it will be shown a multiple response table with the following options:
  - Adverse event(s). In this case, specify the adverse event.

- Pregnancy.
- Abnormal laboratory value(s).
- Abnormal test procedure result(s).
- Unsatisfactory therapeutic effect.
- Study terminated by sponsor.
- Non compliance with study treatment.
- Protocol deviation.
- Physician decision.
- Subject withdrew consent.
- Lost to follow-up.
- Administrative reasons.
- Death.
- Study indication.
- Other. In case of other, specify.

**8 TREATMENT**

- Patients with 16 weeks of treatment who discontinue due to no response
- Patients with treatment in week 36.
- Patients with at least one dose modification (No /Yes). For each dose modification, it will be shown the reasons.
- Duration of treatment (days, from the start date to the end date). If the patient has modified the dose, it will be shown the duration for each dose indicated.

**9 ADVERSE EVENTS**

**This section will be analyzed with Safety Set population.**

The categorical variables to be described are:

- Number of patients with at least one adverse event.
- Number of adverse events per patient.

For total of adverse events, it will be shown:

- Description of event. The event will be codified by MedDRA and will be shown PT and SOC.
- Does the AE meet the definition of serious? (No / Yes).
- Severity (1 / 2 / 3 / 4/ 5).
- AESI (No / Yes).
- Relationship to study drug (Not related / Related).
- Action taken (No action taken / Study drug dosage adjusted / Study drug temporarily interrupted / Study drug permanently discontinued)
- Outcome (Not recovered-Not resolved / Recovered-Resolved / Recovering-Resolving / Recovered with sequelae / Fatal / Unknown).
- Number of patients with different adverse events reported by severity (1 / 2 / 3 / 4 / 5). A list of the different AEs experienced by patients according to the maximum grade, N and % will be presented. (Events will be run by SOC and PT).

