Safety: To evaluate the safety of eltrombopag.	Occurrence, incidence, severity of adverse events (AEs), serious adverse events (SAEs) based on the CTCAE criteria (v 4.03), and reasons for withdrawal from the study including the AEs leading to discontinuation.	Refer to Section 10.5.2

Objective	Endpoint	Analysis
	Physical examination, performance status, height and weight, vital signs, safety laboratory evaluations, ECG and ophthalmological monitoring.	

4 Study design

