8.1.3 Adverse events of special interest

Adverse events of special interest (AESI) are defined as events (serious or non-serious) which are ones of scientific and medical concern specific to the sponsor's product or program, for which ongoing monitoring and rapid communication by the investigator to the sponsor may be appropriate. Such events may require further investigation to characterize and understand them.

Adverse events of special interest are defined by an ongoing review of the safety data. AESIs are discussed in detail in the Investigator Brochure.

The AESIs for this study are:

- Bleeding events
- Hepatobiliary events
- Renal related events
- Cataract-related events
- Thromboembolic events
- Hematological malignancy
- Abnormal bone marrow analysis/cytogenetic abnormality

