10.5.2.2 Adverse events (AEs)

Summary tables for adverse events (AEs) have to include only AEs that started or worsened during the on-treatment period, the **treatment-emergent** AEs (TEAEs). However, all safety data (including those from the pre-and post-treatment periods) will be listed and those collected during the pre-treatment and post-treatment period are to be flagged.

The incidence of TEAEs (new or worsening from baseline) will be summarized by system organ class and or preferred term, severity (based on CTCAE grades), type of adverse event, dose and relation to study treatment

Deaths reportable as SAEs and non-fatal serious adverse events will be listed by patient and tabulated by type of adverse event.

Specific safety event categories (SEC) will be considered. Such categories consist of one or more well-defined safety events which are similar and for which there is a specific clinical interest in connection with the study treatment(s).

For each specified SEC, number and percentage of patients with at least one event part of the SEC will be reported.

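### SAP 9 describes seriousness, special interest and relatedness per event, so it does not specify how many patients had an SAE, a related AE or an event in each special-interest category

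*SAP*

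**What the plan says.** **SAP 9.** The section states "This section will be analyzed with Safety Set population". It opens with two summaries: how many patients had any AE, and how many AEs each patient had. Then, under "For total of adverse events, it will be shown", it lists coded term, seriousness, severity, AESI (Yes/No), "Relationship to study drug (Not related / Related)", action taken (including "Study drug temporarily interrupted / Study drug permanently discontinued") and outcome. It closes with a patient-level table by SOC and PT at maximum grade, with N and %. That table is not split by seriousness, relatedness or AESI.

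**SAP 10.7.** The safety objective is declared covered by SAP 9 (adverse events) and SAP 7 (reasons for not completing the study).

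**SAP 7 and 8.** SAP 7 counts patients who did not complete the study and names the AE where that was the reason. SAP 8 counts patients with a dose modification and gives the reasons.

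**Protocol.** The safety row of Table 3-1 begins "Occurrence, incidence, severity of adverse events (AEs), serious adverse events (SAEs) based on the CTCAE criteria (v 4.03), and reasons for withdrawal". Section 10.5.2.2 asks for treatment-emergent AE incidence by, among other things, relation to treatment. It asks for SAEs to be listed by patient and tabulated by type. It also says "For each specified SEC, number and percentage of patients with at least one event part of the SEC will be reported", where SEC means safety event category. Section 8.1.3, under "The AESIs for this study are", names seven: bleeding, hepatobiliary, renal, cataract, thromboembolic, hematological malignancy, and abnormal marrow or cytogenetic findings.

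**The concern.** An event share and a patient incidence answer different questions. The first depends on how many minor or repeated events were recorded, and so partly on how long patients stayed under observation. The second is the probability that a treated patient is affected, which is what incidence means in the protocol's endpoint.

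The protocol's own risk benchmarks in section 6.2.3 are patient-based: thromboembolic events in 6 of 143 (4%) against 2 of 145 (1%) patients with chronic liver disease, cataract in 8% against 5%, and clonal evolution at 10-15%. A share of events cannot be set beside any of these. A single AESI flag also gives no split between categories as different as bleeding and clonal evolution.

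**Working it through.** The plan states no figure that bears on this point, so there is none to reproduce. The check compares the texts and then uses illustrations with assumed counts.

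**1. What the SAP wording means.** SAP 10.4 uses the same phrasing for transfusions: it sets the number per patient against a description of transfusion type over the total of transfusions. Read the same way, the items in SAP 9 are attributes of events, with the number of events as denominator.

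**2. Protocol quantity against SAP output.**

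| Patient-level quantity | Basis in the protocol | Specified in the SAP? |
|---|---|---|
| Any AE | Table 3-1 | Yes, SAP 9 |
| Each PT by maximum grade | 10.5.2.2 | Yes, SAP 9 |
| At least one SAE | Table 3-1 (incidence of SAEs) | No; event-level flag only |
| At least one related AE | 10.5.2.2 | No; event-level flag only |
| At least one event in each safety event category | 10.5.2.2, with 8.1.3 as the natural list | No; one pooled event-level flag |
| AE leading to permanent drug discontinuation | Table 3-1 (AEs leading to discontinuation) | Partly: study non-completion because of an AE (SAP 7), dose-modification reasons (SAP 8) |

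**3. Can the missing figures be recovered from the event table?** Assume 33 treated patients (the planned enrolment, all dosed), 100 AEs and 10 serious events.
- Event share = serious events / all events = 10/100 = 10%.
- Patient incidence = k/33, where k is the number of patients with at least one SAE. Exact (Clopper-Pearson) two-sided 95% limits are shown.

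| k | Event share | Patient incidence (95% CI) |
|---|---|---|
| 1 | 10% | 3.0% (0.1 to 15.8) |
| 2 | 10% | 6.1% (0.7 to 20.2) |
| 5 | 10% | 15.2% (5.1 to 31.9) |
| 10 | 10% | 30.3% (15.6 to 48.7) |

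Conversely, hold patients fixed: 20 SAEs in 12 of 33 patients is 12/33 = 36.4%. With 5, 10 or 20 AEs per patient the event share is 20/165 = 12.1%, 20/330 = 6.1% or 20/660 = 3.0%. The share moves while the patient incidence does not.

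**4. Can they be recovered from the SOC/PT table?** Not for categories. Suppose a category contains two PTs and each row shows 3 patients. Those rows are compatible with 3 distinct patients (all overlapping) up to 6 (none overlapping), so 3/33 = 9.1% to 6/33 = 18.2%. Nor for SAEs: the table is graded by severity, and Protocol 8.1.2.1 says that a Grade 3 or 4 event is not automatically serious.

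**5. Discontinuation.** The protocol glossary separates permanent cessation of study treatment from premature withdrawal and notes that the two need not coincide. SAP 7 counts the second. SAP 8 counts dose modifications with reasons. Neither specifies the number of patients with an AE that led to permanent drug discontinuation.

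**The case against.** The strongest reply is that SAP 9 is not purely event-level. It counts patients with any AE, gives AEs per patient (which would show up patients with many repeated events), and gives patient N and % for each PT by maximum grade. This stands. A reader might infer that a few thromboembolic events would vanish into a pooled AESI count dominated by bleeding; the documents do not support that, because thrombotic, hepatic and cataract terms would each appear as patient counts in the SOC/PT table. What is missing is the grouped row per category, which cannot be built by adding PT rows.

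A reader might also infer that drug discontinuation for AEs goes unreported by patient. That is too strong. The endpoint in Table 3-1 is worded around reasons for study withdrawal, and SAP 7 and SAP 8 cover much of it. The remaining gap is the narrow one in step 5 of the working.

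Two limits on the protocol side also stand. Section 10.5.2.2 neither lists the safety event categories nor says that they are the seven AESIs. They are defined by specific clinical interest in relation to the treatment, which makes the AESIs the natural reading, but it is an inference. If other categories were intended, the SAP still tabulates none. For SAEs, 10.5.2.2 asks for a listing by patient and a tabulation by type; the case for a patient percentage rests on the word incidence in Table 3-1.

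Finally, the SAP's silence does not cancel the protocol's requirements, and the collected data would allow these counts. The accurate statement is that the SAP does not specify them, not that they will never be produced.

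**Conclusion.** The point holds. As written, the SAP does not specify the number and percentage of patients with at least one SAE, with at least one related AE, or with an event in each special-interest category. It nevertheless treats the safety objective as covered by SAP 9 and SAP 7. It also omits the count of patients with an AE leading to permanent drug discontinuation, though that gap is partly filled elsewhere.

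The conclusion rests on reading the SAP 9 items as event-level, which SAP 10.4 supports, and, for the category rows, on taking the seven AESIs as the protocol's safety event categories. The size in this trial cannot be derived from the documents. The illustrations show only that one event share (10%) is compatible with patient incidences from 3.0% to 30.3% at 33 patients; they do not predict the actual discrepancy. The point concerns safety reporting and leaves the efficacy analysis untouched. It should be corrected before the safety tables are produced.

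**What to change.** In SAP 9, add rows with the Safety Set as denominator, giving n (%) of patients with:
- at least one SAE;
- at least one related AE;
- at least one AE leading to permanent drug discontinuation;
- at least one event in each of the seven AESI categories of Protocol 8.1.3.

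Count each patient once per row and keep the number of events as a second column. State in the SAP that the seven AESIs are the safety event categories of Protocol 10.5.2.2 (or list the categories intended), and include the mapping of MedDRA preferred terms to categories. Exact two-sided 95% intervals for the AESI rows would help at this sample size but are optional; the protocol asks only for number and percentage.

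The cost is changes to table shells plus the term mapping. The mapping is needed because the AE attributes in Protocol 8.1.1 include no AESI category and SAP 9 carries only a Yes/No flag. Seriousness, relatedness and action taken are already recorded for each event, so no new data collection is required.

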## 10 OBJECTIVES ANALYSES

In this section, it will be shown the confidence intervals to 95%.

### 10.1 Primary objective

**To evaluate the efficacy of eltrombopag for poor graft function on overall hematologic response (partial and complete) as determined by platelets, hemoglobin and neutrophil counts, by 16 weeks after the initiation of eltrombopag.**

It will be calculated:

- The overall response rate, defined as the percentage of patients who have a hematological response (partial and complete) by 16 weeks after the initiation of eltrombopag. If the patient hasn't response in that week because was exit from the study before week 16 and in the last evaluation had a partial or complete response, also be considered as responder.

### 10.2 Secondary objective 1

**To determine the response in each hematological lineage separately.**

It will be calculated:

- Percentage of patients who have a partial response in the neutrophil lineage, defined as Absolute neutrophil count (ANC)  $\geq 1,000/\mu\text{L}$  (when pretreatment ANC was  $< 1,000/\mu\text{L}$ ) confirmed in two consecutive blood tests separated a minimum of 7 days.
- Percentage of patients who have a complete response in the neutrophil lineage, defined as Absolute neutrophil count (ANC)  $\geq 1,500/\mu\text{L}$  (when pretreatment ANC was  $< 1,000/\mu\text{L}$ ) confirmed in two consecutive blood tests separated a minimum of 7 days.
- Percentage of patients who have a response in the neutrophil lineage (partial or complete).
- Percentage of patients who have a partial response in the platelet lineage, defined as Platelet count  $\geq 20,000/\mu\text{L}$  (with platelet transfusion independence), confirmed in two consecutive blood tests separated a minimum of 7 days.
- Percentage of patients who have a complete response in the platelet lineage, defined as Platelet count  $\geq 100,000/\mu\text{L}$  (with platelet transfusion independence), confirmed in two consecutive blood tests separated a minimum of 7 days.

- Percentage of patients who have a response in the platelet lineage (partial or complete).
- Percentage of patients who have a partial response in the hemoglobin lineage, defined as Hemoglobin  $\geq 100\text{g/L}$  (when pretreatment Hb was  $<100\text{g/L}$ ) (with red blood cells (RBC) transfusion independence), confirmed in two consecutive blood tests separated a minimum of 7 days.
- Percentage of patients who have a complete response in the hemoglobin lineage, defined as Hemoglobin  $\geq 110\text{g/L}$  (when pretreatment Hb was  $<100\text{g/L}$ ), confirmed in two consecutive blood tests separated a minimum of 7 days.
- Percentage of patients who have a response in the hemoglobin lineage (partial or complete).

Responses in each hematological lineage separately will be determined at weeks 16, 20, 24, 30 and 36 after the initiation of eltrombopag.

In addition,

- To assess if there are statistical significance differences in ANC between baseline and week 24, it will be applied the appropriate paired test (T-test paired or Wilcoxon, depending the distribution of sample).
- To assess if there are statistical significance differences in ANC between baseline and week 36, it will be applied the appropriate paired test (T-test paired or Wilcoxon, depending the distribution of sample).
- To assess if there are statistical significance differences in platelets between baseline and week 24, it will be applied the appropriate paired test (T-test paired or Wilcoxon, depending the distribution of sample).
- To assess if there are statistical significance differences in platelets between baseline and week 36, it will be applied the appropriate paired test (T-test paired or Wilcoxon, depending the distribution of sample).
- To assess if there are statistical significance differences in hemoglobin between baseline and week 24, it will be applied the appropriate paired test (T-test paired or Wilcoxon, depending the distribution of sample).
- To assess if there are statistical significance differences in hemoglobin between baseline and week 36, it will be applied the appropriate paired test (T-test paired or Wilcoxon, depending the distribution of sample).

### 10.3 Secondary objective 2

**To evaluate the long-term efficacy of eltrombopag on overall hematologic response (partial and complete) at 24 and 36 weeks after the initiation of eltrombopag.**

It will be calculated:

- Percentage of patients who have secondary overall hematological response at 24 weeks, defined as the maintenance of a partial or complete response at 24 weeks.
- Percentage of patients who have secondary overall hematological response at 36 weeks, defined as the maintenance of a partial or complete response at 36 weeks.

[figure not shown]
### 10.4 Secondary objective 3

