6.1.2 Treatment duration

The duration of treatment with eltrombopag will be based on the reasons described below and other reasons for early withdrawal ([Section 7.2.3.17.2.3.1](#)):

- If no partial or complete hematological response is observed at 16 weeks and maintained afterwards, the patient will be withdrawn from the study.
- In patients achieving complete response without transfusion support for a minimum of 8 weeks, the dose of eltrombopag may be reduced by 50%, and discontinued if counts remain stable after 8 weeks at the reduced dose. If relapse occurs after eltrombopag discontinuation, eltrombopag can be reintroduced at the last effective dosage.
- If new clonal cytogenetic abnormalities associated with dysplastic bone marrow findings are observed such as monosomy 7, eltrombopag should be permanently discontinued.

- If the patient develops myelodysplastic syndrome (MDS) or acute myeloid leukemia (AML) assessed by sensitive methods, eltrombopag will be permanently discontinued.
- If other non-clonal and/or cytogenetic abnormalities with uncertain meaning not previously observed and not associated with worsening blood counts or bone marrow dysplastic, the decision of discontinuing eltrombopag is up to the investigator, based on a more frequent bone marrow aspirate monitoring of cytogenetic abnormalities and dysplastic findings.
- If relapse of previous hematological disease occurs, eltrombopag will be permanently discontinued.
- If patient receives a new HSCT, eltrombopag will be permanently discontinued

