10.4.1 Variable

The primary variable is the overall hematological response (partial and complete) by 16 weeks after the initiation of eltrombopag. The primary analysis will be assessed based on the FAS.

A partial hematologic response (PR) is defined when **any** of the following:

- Platelet count $\geq 20,000/\mu\text{L}$ (with platelet transfusion independence), confirmed in two consecutive blood tests separated a minimum of 7 days.
- Absolute neutrophil count (ANC) $\geq 1,000/\mu\text{L}$ (when pretreatment ANC was $< 1,000/\mu\text{L}$), confirmed in two consecutive blood tests separated a minimum of 7 days.
- Hemoglobin $\geq 100\text{g/L}$ (when pretreatment Hb was $< 100\text{g/L}$) (with red blood cells (RBC) transfusion independence), confirmed in two consecutive blood tests separated a minimum of 7 days.

A complete hematologic response (CR) is defined when **all three** of the following:

- Platelet count $\geq 100,000/\mu\text{L}$, confirmed in two consecutive blood tests separated a minimum of 7 days.
- Absolute neutrophil count (ANC) $\geq 1,500/\mu\text{L}$ (when pretreatment ANC was $< 1,000/\mu\text{L}$), confirmed in two consecutive blood tests separated a minimum of 7 days.
- Hemoglobin $\geq 110\text{ g/L}$ (when pretreatment Hb was $< 100\text{g/L}$), confirmed in two consecutive blood tests separated a minimum of 7 days.

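### Hemoglobin complete response lacks the transfusion-independence condition that hemoglobin partial response carries, so a transfused patient can count as a hemoglobin-lineage responder; platelet complete response differs between protocol and SAP

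*SAP*

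**What the plan says.** The protocol defines response in its summary, in section 7.3.1.1 and in section 10.4.1, with the same criteria each time. Any one lineage is enough for partial response. The platelet criterion carries the condition "with platelet transfusion independence), confirmed in two consecutive blood tests separated a minimum of 7 days". The hemoglobin criterion carries "with red blood cells (RBC) transfusion independence), confirmed in two consecutive blood tests separated a minimum of 7 days". The paragraph that starts "A complete hematologic response (CR) is defined when" then asks for all three lineages at higher thresholds (platelets 100,000/µL, neutrophils 1,500/µL, hemoglobin 110 g/L), and mentions transfusion for none of them. The lineage endpoints in protocol Table 3-1 take their thresholds from these definitions.

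SAP 10.2 writes out partial and complete response lineage by lineage, then a combined partial-or-complete percentage for each. The bullet opening "Percentage of patients who have a complete response in the platelet lineage, defined as Platelet count" does require platelet transfusion independence. The bullet opening "Percentage of patients who have a complete response in the hemoglobin lineage, defined as Hemoglobin" gives the 110 g/L threshold, the baseline condition and the confirmation rule, and does not mention transfusion.

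Protocol 6.3.1.1 allows platelet and red-cell transfusion whenever medically needed. SAP 10.1 does not restate the overall criteria, so the primary endpoint relies on the protocol's wording.

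**The concern.** A complete response should be a stricter version of a partial response. For hemoglobin it is stricter on the count but looser on transfusion, so the two categories are not nested. Because the SAP counts a patient who meets either one, the looser condition decides whether a transfused patient enters the combined rate.

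Lineage response is the first secondary objective, and SAP 10.2 determines it at weeks 16, 20, 24, 30 and 36. Protocol 2.1 bases the study on the idea that lineages other than platelets may improve on the drug. A hemoglobin response that transfusion alone can produce is weak evidence for that idea.

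The platelet problem is of a different kind: the two documents give different definitions of the same category.

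**Working it through.** **The plan's own figure.** The documents give no figure for the lineage endpoints. The nearest is the sample-size statement in protocol 10.7: n = 33, 45% observed, one-sided 95% lower limit 30.1%, distance 14.9 points. With x = 0.45 × 33 = 14.85, the Clopper-Pearson limit is the 0.05 quantile of Beta(x, n − x + 1). This gives 30.08%, a distance of 14.92 points, so the figure reproduces. Nothing below changes it.

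**Step 1: is transfusion independence required?**

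| Criterion | Protocol (summary, 7.3.1.1, 10.4.1) | SAP 10.2 |
|---|---|---|
| Platelets, partial (20,000/µL) | yes | yes |
| Platelets, complete (100,000/µL) | **no** | yes |
| Hemoglobin, partial (100 g/L) | yes | yes |
| Hemoglobin, complete (110 g/L) | **no** | **no** |
| Neutrophils, partial and complete | no | no |

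**Step 2: does complete imply partial within a lineage?** It does only if the complete criterion has a higher threshold and keeps every condition of the partial one.

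- Neutrophils: 1,500 exceeds 1,000, the baseline condition is the same, and no transfusion condition applies. Nested in both documents.
- Platelets: nested in the SAP, not in the protocol.
- Hemoglobin: not nested in either document.

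**Step 3: an example.** Take baseline hemoglobin below 100 g/L, red-cell transfusions continuing, and results of 112 and 111 g/L one week apart. Partial: the count is met, transfusion independence is not, so the patient fails. Complete: both values are at least 110, the baseline condition is met and the confirmation is met, so the patient passes. Partial or complete: counted as a responder.

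**Step 4: size.** SAP section 4 puts all analyses except adverse events on the Full Analysis Set. With the planned 33 patients and no missing data, one misclassified patient moves the rate by 1/33 = 3.0 percentage points. The number of such patients is unknown.

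**Step 5: does it reach the overall response?** Overall complete response needs all three lineages; partial response needs one.

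- Baseline neutrophils below 1,000/µL: a complete responder has at least 1,500/µL and so already meets the neutrophil partial criterion, which has no transfusion condition. The patient is a responder either way.
- Baseline neutrophils 1,000/µL or more: eligibility then requires hemoglobin below 100 g/L. If the parenthetical neutrophil condition is read as a requirement, complete response is impossible. If it is read as waived, a patient can be complete without being partial only when receiving both platelet and red-cell transfusions.

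Enumerating baseline neutrophil and hemoglobin status, both transfusion types and both readings of the parenthesis leaves that last combination as the only exception.

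**The case against.** The strongest defense is that transfusion independence is understood in any complete response. The text does not support it. Protocol 6.1.2 speaks of "In patients achieving complete response without transfusion support for a minimum of 8 weeks", which adds freedom from transfusion as something beyond complete response. The SAP writes the condition out for platelet complete response and omits it for hemoglobin, so a programmer following the text would apply it to one and not the other.

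The second defense is that the consequence is limited, and this stands. Protocol 10.4.2 sets no hypotheses, 10.8 plans no power for secondary variables, and SAP 10.4 tabulates transfusions by type and number before treatment and before and after week 16. That table makes transfusion use visible but does not correct the hemoglobin rate. The affected group could also be empty, since a patient must reach 110 g/L on two consecutive tests while still being transfused.

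Three stronger readings are tempting, and the documents do not support them:

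- A reader might infer that the primary rate is inflated, noting that 15/33 gives a lower limit of 30.5% and 14/33 gives 27.8%, so one patient could decide the comparison with 30%. Step 5 shows that this needs the single narrow combination described there.
- A reader might divide by only those patients anemic at baseline and get a larger shift per patient. Neither document restricts the denominator that way. Protocol 10.5.1 refers to a valid percentage, which SAP section 3 defines as excluding missing values only.
- A reader might infer that the planned platelet-lineage rate is inflated. SAP 10.2, which specifies that analysis, already has the condition.

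**Conclusion.** The point holds for the hemoglobin lineage. As written, the SAP's complete and combined hemoglobin response rates can include patients whose counts are maintained by red-cell transfusion, at 3.0 points per patient. That size assumes a Full Analysis Set of 33 with complete data. For platelets, the finding is a disagreement between protocol and SAP that must be reconciled, with no inflation of the analysis the SAP plans. The primary overall response rate is essentially protected by the all-three-lineages rule and by the neutrophil partial criterion.

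One gap affects partial and complete response alike: neither document says how long a patient must be free of transfusion to be transfusion independent. The 7-day minimum between confirmatory tests is a rule about blood tests and should not be taken to supply that period.

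This should be corrected before analysis. It does not threaten the trial's main conclusion.

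**What to change.** 1. In SAP 10.2, add red-cell transfusion independence to hemoglobin complete response. Every lineage complete response in the SAP then also satisfies the partial one.
2. Reconcile the platelet and hemoglobin complete-response definitions in the protocol (summary, 7.3.1.1, 10.4.1) with the SAP for analysis purposes.
3. Have the sponsor state, before analysis, one transfusion-free period that defines transfusion independence, and apply it identically to partial and complete response. The documents give no basis for choosing its length, so none is proposed here.

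**Cost.** No new data, visits or patients are needed: transfusions are already recorded (protocol 6.3 and 7.3.1.2; SAP 10.4), and n = 33 and the 30.1% limit are unchanged. The hemoglobin complete and lineage response rates may come out slightly lower. The hemoglobin analysis gap can be closed in the SAP alone; changing protocol text requires a written amendment with the approvals listed in protocol 12.1.

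The response criteria also feed the treatment-continuation rule (protocol 4.1 and 7.2.2) and the dose-reduction rule (protocol 6.1.2). The sponsor should reconcile those sections with whatever definition is adopted; no clinical rule is proposed here.
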